#### D.6. Removal from the Ventilator Management Protocol

Patients may be removed from the 6 ml/kg PBW tidal volume ventilation requirement if they develop neurologic conditions where hypercapnia would be contraindicated (e.g., intracranial bleeding, GCS < 8, cerebral edema, mass effect [midline shift on CT scan], papilledema, intracranial pressure monitoring, fixed pupils).

# **APPENDIX E:** Conservative Fluid Management Approach

This fluid protocol captures the primary positive outcome of the FACTT trial on increasing ventilator free days. For patients with a CVC, this protocol should be initiated within four hours of randomization in enrolled patients, and continued until UAB or study day 7, whichever occurs first.

- 1. Discontinue maintenance fluids.
- 2. Continue medications and nutrition.
- 3. Manage electrolytes and blood products per usual practice.
- For shock, use any combination of fluid boluses# and vasopressor(s) to achieve MAP ≥ 60 mmHg as fast as possible. Wean vasopressors as tolerated beginning four hours after blood pressure has stabilized.
- 5. Withhold diuretic therapy in renal failure § and until 12 hours after last fluid bolus or vasopressor given.

For patients without a CVC, no fluid gain over the first 7 study days is recommended once patients' the blood pressure has stabilized. Stable blood pressure is defined as no requirement for either vasopressors or a fluid bolus to support blood pressure for 12 or more hours.

CVP	PAOP	MAP $\geq$ 60 mm Hg AND off vasopressors for $\geq$ 12 hours					
(recommended)	(optional)	Average urine output < 0.5 ml/kg/hr	Average urine output > 0.5 ml/kg/hr				
>8	> 12	Furosemide* Reassess in 1 hour	Furosemide*				
4-8	8-12	Give fluid bolus as fast as possible#	Reassess in 4 hours				
< 4	< 8	Reassess in 1 hour	No intervention Reassess in 4 hours				

Renal failure is defined as dialysis dependence, oliguria with serum creatinine > 3mg/dl, or oliguria with serum creatinine 0-3 with urinary indices indicative of acute renal failure.

# Recommended fluid bolus= 15 mL / kg crystalloid (round to nearest 250 mL) or 1 Unit packed red cells or 25 grams albumin

\* Recommended Furosemide dosing = begin with 20 mg bolus or 3 mg / hr infusion or last known effective dose. Double each subsequent dose until goal achieved (oliguria reversal or intravascular pressure target) or maximum infusion rate of 24 mg / hr or 160 mg bolus reached. Do not exceed 620 mg/day. Also, if patient has heart failure, consider treatment with dobutamine.

# **APPENDIX F:** Time-Events Schedule

Measurement/Event	Day 0	1	2	3	4	5	6	7	8	9	10	12	14	21	28	60/ 90
Demographics, History & Physical, Height, Weight	Х															
AUDIT and smoking survey	Х															
Etiology of ARDS, site of sepsis	Х															
APACHE III Score	Х															
Brussels Score^	Х	X	х	х	Х	Х	Х	X	х	Х	Х	Х	Х			
GCS	Х							X					Х			
Ventilator Parameters (including FiO 2 ) *	Х	X	х	х	х			X				Х		X	х	
Arterial Blood Gases (PaO 2 , PaCO 2 , pH) and SpO 2	Х	A	A	А	A	А	А	Α					А	А	A	
Vital signs *	X	X	Х	Х	X	Х	X	X								
Blood Statin peak/trough level $^{\beta}$							Х									
Concomitant medications (Y/N)	Х	X	х	х	Х	Х	Х	X	Х	Х	Х					
Presence of myopathy €																
I/Os	Х	X	х	х	Х	Х	Х	X								
Occurrences of MI, VTE, ischemic stroke, bowel ischemia €																
Episodes of arrhythmias $^{\Omega}$	Х	X	Х	Х	Х	Х	Х	X	Х	Х	Х	Х	Х			
ALT β	Х	X	А	Х	А	А	Х	А	А	А	А	А	Х	X		
СК, β	Х	X	А	Х	А	А	Х	Α	А	Α	Х	А	Х	X		
AST	Х	х	А	х	А	А	х	А	А	Α	А	А	Х	Х		
Chest X-ray (LIS)	х	A	А	А	А	А	А	А	А	А	А					
Plasma CRP levels $^{\beta}$	Х						Х						Х			
Blood for DNA	Х															
Blood and Urine for markers of inflammation $^{\beta}$	Х			Х			х									
Study Drug Administration Record	Х	X	х	Х	х	Х	х	X	Х	Х	Х	Х	Х	X	х	
Vital Status															X	Х

X = Required

A=When available

\*Data gathered at times indicated or until patient achieves 48 hrs of unassisted breathing, whichever is sooner

€ Data gathered until 72 hours after study drug is discontinued

^Daily for 14 days or until ICU discharge and the date and value of the highest creatinine between day 15 and 28

 $^{\Omega}$  Data gathered until day 14 or ICU discharge, whichever occurs first

β These may be obtained plus or minus two days except for baseline and day 1. Attempt to maintain spacing between labs and samples if obtaining on days other than those specified.

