#### Secondary Efficacy Variables:

- 1. Ventilator Free Days to day 28
- 2. Hospital mortality to day 28
- 3. Organ failure free days at day 14
- 4. ICU-free days at day 28
- 5. Hospital-free days at day 60

- 6. Increase in PaO2/FiO2 ratio and reduction in Oxygenation Index on study days 1-7 (to use ABGs as available)
- 7. Venous thromboembolism (VTE) to day 14
  - a. Documented by venous ultrasound, impedance plethysmography, contrast venography, ventilation-perfusion lung scan, CTPA/V, or pulmonary angiography
- 8. Composite end-point of myocardial infarction, bowel ischemia or ischemic stroke to study day 28
- 9. Arrhythmias during ICU stay or until day 14, whichever is first
- 10. Development of acute kidney injury (AKI)
- 11. Changes in plasma concentrations of CRP from day 0 to day 6 and day 14. Blood and urine will be reserved beyond study completion for additional biomarker studies.

**Focused Safety Analysis:** Incidence of elevations in CK > 10 times ULN or ALT > 8 times ULN as measured on days 0,1,3,6,14,21 (Appendix B)

**Study Drug Dosing:** All study drug doses will be administered via the enteric or oral route. Study drug will be blinded using an identical appearing placebo.

- 1. The first study drug dose (rosuvastatin or placebo) will be administered within 4 hours of randomization as a loading dose of 40 mg.
- 2. Subsequent doses will be at 10 am daily (+/- 4 hours) starting on the next calendar day as a maintenance dose of 20 mg.
  - a. If for any reason a maintenance dose is not administered at the intended time, it may be administered subsequently but not more than 12 hours after the intended time of administration.

Should the time be > 12 hours since last scheduled dose, the patient will not receive a dose on that study day but will be given a loading dose on the next calendar day. Maintenance dosing will continue on subsequent days.

Daily doses will be reduced by 50% for patients with a creatinine level of greater than or equal to 2.8 mg/dL who are not on renal replacement therapy. Loading doses will not be reduced.

Daily Dosing:

- Each subject will receive full dose if last known creatinine value is less than 2.8 mg/dL.
- Each subject will receive half dose if last known creatinine value is greater than or equal to 2.8 mg/dL (unless receiving renal replacement therapy in which case a full dose is given).

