# 3. End-Points

Analysis of the primary, secondary and other endpoints will be conducted on an intention-totreat (as randomized) basis.

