#### 3.3. Other Secondary Endpoints

- 1. Hospital mortality to day 28
- 2. Organ failure free days at day 14
- 3. ICU-free days at day 28
- 4. Hospital-free days at day 60
- 5. Increase in PaO2/FiO2 ratio and Oxygenation Index on study days 1-7

- 6. VTE at day 14
  - a) Documented by venous ultrasound, impedance plethysmography, contrast venography, ventilation-perfusion lung scan, CTPA/V, or pulmonary angiography
- Composite end-point of myocardial infarction, bowel ischemia or ischemic stroke to day 28
- 8. Arrhythmias during ICU stay or day 14, whichever is first
- 9. Development of acute kidney injury
- 10. Changes in plasma concentrations of CRP from day 0 to day 6 and 14. Blood and urine will be reserved beyond study completion for additional biomarker studies.

The rationale for the primary and first secondary endpoint is given in section 1.9. VTE is an endpoint because statins have been reported to be associated with lower rates of VTE in ambulatory patients. Cardiovascular endpoints are being assessed given the high prevalence of occult cardiovascular disease and the known benefits of statins in this population. The development of AKI is an endpoint as observational studies suggest statins prevent AKI. CRP is a surrogate marker of systemic inflammation and is expected to be reduced by statins.

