# 3.4. Definition of Organ Failure:

Organ failure days are defined according to the most abnormal vital sign or lab value for each calendar day, according to the Brussels Organ Failure Table using the clinically significant organ failure thresholds. Patients will be followed for development of organ failures to death, hospital discharge or study day 14, whichever comes first. Each day a patient is alive and free of an organ failure will be scored as an organ failure-free day. Any day that a patient is alive and free of all 5 organ failures will represent days alive and free of all organ failure.

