#### 5.4. Premature Withdrawal from Treatment

The study drug will be discontinued if a patient develops an increase in either CK > 10 times ULN, AST > 8 times ULN, or ALT > 8 times the ULN, or if patient develops an intraparenchymal CNS bleed. Study drug will also be discontinued if niacin, fenofibrate, cyclosporine, gemfibrozil, lopinavir, ritonavir, atazanavir, daptomycin are administered, or if primary care team or surrogate decision maker request. Data collection will continue on these patients, including the type and dose of any statin used as part of usual care following withdrawal of study drug.

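### Recording of MI, ischemic stroke, bowel ischemia and VTE stops 72 hours after study drug ends, but these secondary endpoints run to day 28 (composite) and day 14 (VTE) as randomized

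*Protocol*

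**What the plan says.** **Endpoint definitions.** Part I lists "Composite end-point of myocardial infarction, bowel ischemia or ischemic stroke to study day 28" and "Venous thromboembolism (VTE) to day 14". Section 3.3 repeats both windows, the first as "Composite end-point of myocardial infarction, bowel ischemia or ischemic stroke to day 28". Section 3 says that analysis of all endpoints "will be conducted on an intention-totreat (as randomized) basis".

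**Recording rule.** The Appendix F row for these events has no day marks. It has only a footnote symbol, shared with the myopathy row: "Data gathered until 72 hours after study drug is discontinued".

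**When drug stops.** Section 5.3 ends study drug at the earliest of day 28, three days after ICU discharge, discharge from the study hospital, or death. Section 5.4 ends it sooner for CK, AST or ALT above threshold, an intraparenchymal bleed, an interacting drug, or on request. It then adds "Data collection will continue on these patients", without naming an endpoint or an end day.

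**A third rule.** Section 6.3 lists these events among its data items. Its general rule is recording on the Appendix F days or until death, ICU discharge or 48 hours of unassisted ventilation.

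**Organ failure.** Section 3.4 says "Patients will be followed for development of organ failures to death, hospital discharge or study day 14, whichever comes first". Sections 6.3 and 6.5 ask for Brussels data for days 0 to 14. The Brussels footnote in Appendix F says "Daily for 14 days or until ICU discharge".

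**The concern.** An endpoint with a fixed window, analysed as randomized, needs every patient observed over that window whatever happens to treatment. Here the event-specific rule closes observation on a date set by drug exposure, and in routine use that date is set by ICU discharge. Both come after randomization and both may respond to treatment.

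Two things are at stake. Events that fall inside the endpoint window but after recording ends may never reach the case report form, which costs information in both arms. And if rosuvastatin shortens or lengthens ICU stay, the arms are watched for different lengths of time, so event proportions can differ with no true effect. An event that was never collected may not be recoverable at analysis, so this belongs in the data-collection instructions.

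**Working it through.** The protocol gives no figure to reproduce here; the check is window arithmetic.

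**Inputs.** Composite to day 28 and VTE to day 14 (Part I, section 3.3). Drug stops at ICU discharge day D plus 3, at most day 28 (section 5.3). Recording ends 3 days after drug stops (Appendix F). D is the ICU discharge that ends dosing, with no earlier withdrawal, hospital discharge or death.

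**Formulas.**
- Recording ends: E = min(28, D + 3) + 3
- Composite days unrecorded: max(0, 28 − E)
- VTE days unrecorded: max(0, 14 − E)

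| ICU discharge (D) | Drug stops | Recording ends (E) | Composite days unrecorded | VTE days unrecorded |
|---|---|---|---|---|
| 5 | 8 | 11 | 17 of 28 | 3 of 14 |
| 7 | 10 | 13 | 15 of 28 | 1 of 14 |
| 8 | 11 | 14 | 14 of 28 | 0 |
| 10 | 13 | 16 | 12 of 28 | 0 |
| 14 | 17 | 20 | 8 of 28 | 0 |
| 22 | 25 | 28 | 0 | 0 |

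The composite is fully covered only if D is 22 or later; VTE is fully covered if D is 8 or later.

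**Can unequal windows create a difference?** The assumptions here are not in the protocol: the same constant hazard λ in both arms, 0.002 to 0.005 per day; and active-arm ICU discharge 2.25 days earlier, borrowing the ventilator-free-day effect in section 7.2. Recorded risk = 1 − exp(−λ × min(28, D + 6)).
- λ = 0.002, control D = 8: control window 14 days, risk 0.028; active window 11.75 days, risk 0.023; ratio 0.84.
- λ = 0.005, control D = 20: control window 26 days, risk 0.122; active window 23.75 days, risk 0.112; ratio 0.92.

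So a ratio of about 0.84 to 0.92 can appear with no true effect. Reverse the assumption, so that the active arm leaves the ICU 2.25 days later than a control D of 8, and at λ = 0.002 the ratio is (1 − exp(−0.0325)) / (1 − exp(−0.028)) = 0.0320 / 0.0276, about 1.16. The example shows that the mechanism works, not how large the bias is or which way it runs.

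**Premature stops.** Read alone, the footnote ends recording on day 6 after a stop on day 3. Section 5.4 says collection goes on. The two texts conflict, so no number of lost days can be assigned to these patients.

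**Organ failure.** For a patient who leaves the ICU on day 5 and is still in hospital on day 14, section 3.4 runs to day 14 while the Brussels footnote stops on day 5: 14 − 5 = 9 days apart.

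**The case against.** **Other provisions may capture the events.** Section 5.4 continues data collection, section 11 has adverse experiences assessed daily to day 28 or hospital discharge, and Appendix G requires record review through the study period. Some events would be caught this way. But section 5.4 covers only premature withdrawal, not patients who finish drug normally after ICU discharge. Adverse event reporting leaves out events expected in ALI unless they are thought study-related or are unusually severe or frequent. Neither is systematic endpoint capture.

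**Blinding and placebo control.** If rosuvastatin changes neither ICU stay nor stop rates, the window distribution is the same in both arms and the cost is lost events and precision. This stands: differential bias is possible, not shown.

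**Stronger readings that a reader might infer.**
- *That toxicity stops shorten the active arm's window and flatter rosuvastatin.* Section 5.4 contradicts the footnote for exactly these patients, and the protocol gives no stop rates by arm. The rates it does cite, from other populations, are low: CK above tenfold in under 0.1% on rosuvastatin (sections 1.7 and 9.1), and liver enzymes above 3 times ULN in under 1% on any statin (Appendix B), against a stop threshold of 8 times.
- *That 14 of 28 days unrecorded means half the events lost.* These are calendar days. Equating them with events needs a constant hazard from ICU through recovery, and some of the days may follow death or discharge home.
- *That unrecorded days will be scored event-free.* The protocol states no such rule; handling of incomplete follow-up may sit in the analysis plan, which is not at hand.

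**Conclusion.** The conflict is real and rests on the text alone. The event-specific recording rule ends on a drug-dependent date, while the endpoints have fixed windows under intention to treat, and no other section cures this for patients who complete drug normally. Recording ends about six days after ICU discharge, so the composite is under-observed for ICU discharge before day 22 and VTE for discharge before day 8, barring earlier hospital discharge or withdrawal. For premature stops the finding is an internal contradiction between Appendix F and section 5.4, with section 6.3 adding a third rule. The Brussels mismatch is a separate inconsistency of the same kind.

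The size and direction of any bias cannot be computed, because the protocol gives no event rates, ICU stay or stop rates by arm. Mortality to day 60 and ventilator-free days are unaffected. This should be fixed, but it does not threaten the trial's main conclusion.

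**What to change.** - Reconcile sections 3.3, 5.4, 6.3 and Appendix F to one recording window counted from randomization: day 28 for the composite and day 14 for VTE, independent of study-drug and ICU status. The 72-hour rule can stay for myopathy, which shares the footnote.
- If recording has to end at hospital discharge or discharge home, define these endpoints explicitly as in-hospital events and report follow-up time by arm, because discharge is itself a post-randomization date.
- Align the Brussels footnote with section 3.4, and make the general stop rule in section 6.3 agree with both.

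The cost is a changed case report form instruction and some extra ward-chart review. The protocol already reaches past ICU discharge for other items: the highest creatinine for days 15 to 28, and ventilator-free days to day 28 even after transfer. Sample size and treatment rules do not change. The change should precede data collection.

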# APPENDIX G: Adverse Events

#### **Procedures for Reporting Adverse Events**

- 1. Assuring patient safety is an essential component of this protocol. Each participating investigator has primary responsibility for the safety of the individual participants under his or her care. The Principal Investigator will evaluate all adverse events. The Study Coordinator must view patient records for possible adverse events throughout the study period. All adverse events occurring within the study period must be reported in the participants' case report forms.
- 2. Investigators will report all *serious, unexpected, AND study-related* adverse events to the Clinical Coordinating Center within 24 hours by fax, phone or email. The local Institutional Review Board must also be notified in a timely manner. The investigator will then submit a detailed written report to the Clinical Coordinating Center and the local Institutional Review Board no later than 5 calendar days after the investigator discovers the event.
- 3. Definitions of Adverse Events
  - a. A *serious* adverse event is any event that is fatal or immediately life threatening, is permanently disabling, or severely incapacitating, or requires or prolongs inpatient hospitalization. Important medical events that may not result in death, be life threatening, or require hospitalization may be considered serious adverse events when, based upon appropriate medical judgment, they may jeopardize the patient or subject and may require medical or surgical intervention to prevent one of the outcomes listed above.
    - i. Life-threatening means that the patient was, in the view of the investigator, at immediate risk of death from the reaction as it occurred. This definition does not include a reaction that, had it occurred in a more serious form, might have caused death. Assessment of the cause of the event has no bearing on the assessment of the event's severity.
  - b. An *unexpected* event is any experience not identified by the type, severity, or frequency in the current study protocol or an event that is unexpected in the course of treatment for ALI or ARDS.
  - c. Adverse events will be considered to be study-related if the event follows a reasonable temporal sequence from a study procedure and could readily have been produced by the study procedure.
  - d. Organ failures or death related to ALI or ARDS or the patient's underlying condition that are systematically captured by the protocol should not be reported as adverse events *unless they are considered to be study related*.

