#### For this trial, a *reportable adverse event* is defined as:

- 1. Any clinically important untoward medical occurrence in a patient receiving study drug or undergoing study procedures which is different from what is expected in the clinical course of a patient with ALI, or,
- 2. Any clinically important, untoward medical occurrence that is thought to be associated with the study drug or procedures, regardless of the "expectedness" of the event for the course of a patient with ALI.
- The following will be reported as adverse events: CK> 10 times ULN ALT > 8 times ULN AST > 8 times ULN Intraparenchymal CNS bleed

*Expected events for ALI* are untoward clinical occurrences that are perceived by the investigator to occur with reasonable frequency in the day to day care of patients with ALI treated in an intensive care unit with mechanical ventilation. Examples of adverse events that are expected in the course of ALI include transient hypoxemia, agitation, delirium, nosocomial infections, skin breakdown, and gastrointestinal bleeding. Such events, which are often the focus of prevention efforts as part of usual ICU care, will not be considered reportable adverse events unless the event is considered by the investigator to be associated with the study drug or procedures, or unexpectedly severe or frequent for an individual patient with ALI. Examples of unexpectedly frequent adverse events would be repeated episodes of unexplained hypoxemia. This would be in contrast to an isolated episode of transient hypoxemia (e.g.  $Sp0_2 \sim 85\%$ ), related to positioning or suctioning. This latter event would not be considered unexpected by nature, severity or frequency.

Investigators will report all events that are **serious** AND **unexpected** AND **study-related**, as defined in Appendix G, to the Clinical Coordinating Center by phone, fax or email within 24 hours of becoming aware of event. The local Institutional Review Board must also be notified in a timely manner. The investigator will then submit a detailed written report to the Clinical Coordinating Center and the Institutional Review Board no later than 5 calendar days after the investigator discovers the event.

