The Clinical Coordinating Center will report all serious, unexpected, and study-related adverse events to the DSMB, by email, or telephone, within 7 calendar days of the CCC being notified of the event. A written report will be sent to the DSMB within 15 calendar days, and these reports will be sent to investigators for submission to their respective Institutional Review Boards. The DSMB will also review all adverse events during scheduled interim analyses. The Clinical Coordinating Center will distribute the written summary of the DSMB's periodic review of adverse events to investigators for submission to their respective Institutional Review Boards in accordance with NIH guidelines.

The Clinical Coordinating Center will also determine if the serious adverse event is unexpected for a statin. Unexpected for a statin is defined as any event not listed in the rosuvastatin package insert. If the Clinical Coordinating Center determines that any serious and study-related adverse event is unexpected for a statin, the FDA will be notified within 7 calendar days. Such events may also meet the definition of Unanticipated Problems as described below.

Investigators must also report Unanticipated Problems, regardless of severity, associated with the study drug or study procedures within 24 hours. An unanticipated problem is defined as follows:

**Unanticipated Problem (UP):** any incident, experience, or outcome that meets all of the following criteria:

- Unexpected, in terms of nature, severity, or frequency, given the research procedures that are described in the protocol-related documents, such as the IRB-approved research protocol and informed consent document; and the characteristics of the subject population being studied;
- Related or possibly related to participation in the research, in this guidance document, possibly related means there is a reasonable possibility that the incident, experience, or outcome may have been caused by the procedures involved in the research;
- Suggests that the research places subjects or others at a greater risk of harm (including physical, psychological, economic, or social harm) than was previously known or recognized.

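### A serious, drug-attributed event that the protocol identifies and ALI makes expected has no expedited route to the Coordinating Center, even when it would require FDA notice

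*Protocol*

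**What the plan says.** **Site report.** Section 11 limits the expedited report to events that are serious, unexpected and study-related. It gives the source of these terms and the deadline: "as defined in Appendix G, to the Clinical Coordinating Center by phone, fax or email within 24 hours of becoming aware of event". Appendix G item 2 repeats the rule.

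**Unexpected, for the site.** Appendix G item 3b has two limbs joined by *or*. The definition runs: "event is any experience not identified by the type, severity, or frequency in the current study protocol or an event that is unexpected". The second limb takes the disease course as its reference and reads in full "an event that is unexpected in the course of treatment for ALI or ARDS". Section 11 gives examples of what is expected in ALI: "transient hypoxemia, agitation, delirium, nosocomial infections, skin breakdown, and gastrointestinal bleeding".

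**Unexpected, for the FDA.** Section 11 has the Coordinating Center judge serious events against the rosuvastatin package insert. If the Center "determines that any serious and study-related adverse event is unexpected for a statin, the FDA will be notified within 7 calendar days". This rule does not mention ALI.

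**DSMB.** Expedited events go to the DSMB within 7 calendar days of the Center being told. For the rest, "The DSMB will also review all adverse events during scheduled interim analyses".

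**The concern.** The site and the Coordinating Center judge expectedness against different references. The site asks whether the event is new to this protocol or to ALI. The Center asks whether it is new to the drug label. The Center's duty to the FDA runs in days, but its only expedited feed of adverse events has already been filtered by the site's question.

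The two tests part company for complications that a ventilated septic patient may have anyway. Suppose an investigator believes that study drug caused one of these. The event may be absent from the label and so notifiable, yet the site has no duty to tell the Center quickly. A drug effect that looks like the disease is also hard to recognize case by case, so slow arrival matters more for these events than for an obviously unusual one.

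**Working it through.** The protocol gives no figure for this point, so there is none to reproduce. The check has three parts.

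**1. The two rules compared.** Take an event already judged serious and study-related. Let A = identified in the protocol by type, severity or frequency (Appendix G 3b, first limb), B = expected in the ALI/ARDS course (second limb), and C = listed in the package insert (Section 11).

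- 24-hour report due = (not A) or (not B)
- FDA notice due = not C

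| A | B | C | 24-hour report | FDA notice |
|---|---|---|---|---|
| yes | yes | yes | no | no |
| yes | yes | no | **no** | **yes** |
| yes | no | yes | yes | no |
| yes | no | no | yes | yes |
| no | yes | yes | yes | no |
| no | yes | no | yes | yes |
| no | no | yes | yes | no |
| no | no | no | yes | yes |

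On the literal *or*, 1 of 8 combinations needs FDA notice without a 24-hour report: identified in the protocol, expected in ALI, not in the insert. If a site lets ALI expectedness decide alone, the sixth row joins it and the count is 2 of 8. These are logical cases, not event frequencies.

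A nosocomial infection or GI bleed that prolongs hospitalization meets the seriousness definition in Appendix G 3a. Section 11 names both as expected in ALI. Unless unusually severe or frequent, such an event fails both limbs.

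**2. Do other clauses supply a deadline?**

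- Section 11, second definition of a reportable adverse event: drug-associated events are reportable whether or not expected. No expedited deadline is set.
- Appendix G 3d: study-related organ failures and deaths return to adverse event reporting. No expedited deadline is set.
- Unanticipated Problems (Section 11): 24 hours, but the event must again be unexpected, judged partly on the population under study.
- Section 8.1: data reach the Center by routine transfer on a prescribed basis, with no event-driven deadline.

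None closes the gap.

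**3. Longest wait for DSMB review.** Inputs: maximum of 1000 patients over 2-3 years, i.e. 24-36 months (Section 4.1); looks at 100, 250, 500 and 750 patients and a final analysis at 1000 (Section 7.2). Assumption: even accrual. Wait = (patients in the interval / 1000) x 24 to 36 months.

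- Start to 100: 100/1000 x 24 to 36 = 2.4 to 3.6 months
- 100 to 250: 150/1000 x 24 to 36 = 3.6 to 5.4 months
- Each later interval: 250/1000 x 24 to 36 = 6 to 9 months

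These are full intervals. An event at mid-interval waits half as long. An expedited event takes at most 24 hours to reach the Center plus 7 calendar days to reach the DSMB.

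**The case against.** The strongest reply is that the gap is narrow and nothing is lost. Four parts of it deserve an answer.

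**The FDA rule is not gated.** A reader might infer that the FDA test can work only on events that pass the site's filter. The text does not say so. The rule covers any serious and study-related event, and the Center also receives case report form data, including drug-associated events that are expected in ALI. This stands: the test remains available, and only the feed is slower.

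**Severe cases may still be expedited.** A reader might infer that a fatal infection, a fatal bleed or drug-attributed hepatic failure escapes the 24-hour report. The *or* in Appendix G 3b does not support that. Section 11 names infection and bleeding by type and takes unexpectedly severe or frequent cases out of its exemption, so a fatal case may count as unexpected. Hepatic failure is not among Section 11's examples, and Appendix B describes acute hepatic failure with statins as very rare. This also stands, and the point rests on the ordinary serious case.

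**No specific event is shown to fall in the gap.** The package insert is not part of the documents, so nobody can check from them whether infection or bleeding is listed. That limits what can be said about frequency, but the two rules still use different references. Nor does the point need statins to cause infection. Section 1.5 presents immune modulation as a possible benefit, and Section 1.2 cites one cohort with no nosocomial bacteremia among statin users.

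**Single-case reports do not replace comparison by arm.** True. The DSMB reviews all adverse events at its looks, and organ failure and enzyme elevations are collected systematically. Expedited reporting serves a different purpose: it gets an event that the investigator already attributes to the drug to the body that must decide on notice.

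**Conclusion.** The mismatch holds in a limited form. A serious, drug-attributed event that the protocol identifies and that is expected in ALI has no expedited route from site to Coordinating Center, even when its absence from the package insert would require FDA notice. That is 1 of 8 logical combinations on the literal definition, or 2 of 8 if ALI expectedness is applied alone.

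The consequence is delay, not non-reporting. The event waits for routine transfer to reach the Center, and its only stated DSMB review is at the next scheduled look. The upper limits of 2.4-3.6, 3.6-5.4 and 6-9 months assume even accrual over 2-3 years and a look held when its patient count is reached. They describe DSMB delay. Delay to the FDA depends on the transfer interval, which the protocol does not give.

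This is a modest defect in the reporting rules. It does not affect the efficacy analysis, and it is worth correcting because the correction is cheap.

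**What to change.** In Section 11 and Appendix G item 2, make the 24-hour report due for any event that is serious and study-related, whatever its expectedness in ALI. The Coordinating Center then applies both tests, ALI course and package insert, to decide on DSMB and FDA reporting. With this trigger, the combinations needing FDA notice without a 24-hour report fall to 0 of 8. Unrelated events that are expected in ALI stay exempt, as now.

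In the same edit, align Appendix G 3c with Section 11. The appendix defines study-relatedness by study procedure alone, while Section 11 refers to study drug or procedures. Without that change, a literal reader could still leave drug-caused events outside the trigger.

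The cost is a wording change in these places and a few more expedited forms, limited to serious events that the investigator has already judged related.
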